4.3 DOSING AND DOSE ESCALATION

This is a dose-escalation study in which 6 doses of NAC effervescent tablets are being tested: 600mg bid, 600mg tid, 1200mg bid, 1200mg tid, 1800mg bid and 1800mg tid. Patients will be given the dose pre-determined for the cohort they enter upon enrollment. The most common side effect of NAC is nausea and vomiting. If a patient cannot tolerate the assigned dose of NAC due to nausea and/or vomiting, the dose will be reduced to the dose immediately below the current dose. If that dose cannot be tolerated, the dose will be reduced to the next lowest level. This will be done until a tolerated dose is identified and the patient will be maintained on that dose throughout the trial. If a patient cannot tolerate the starting dose of 600mg bid, they will be reduced to 600mg qd. If a patient cannot tolerate a dose of 600mg qd, they will be exited from the trial. If 3 of the first 5 subjects in a cohort or a total of 5 subjects are unable to tolerate a particular dose of NAC, no additional subjects will be treated with that dose and the dose immediately below it will be designated the maximum tolerated dose. All subsequent subjects enrolled in the study will be treated with the maximum tolerated dose.

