Oxidative damage has been implicated in several diseases including cystic fibrosis, chronic obstructive pulmonary disease (COPD), and Idiopathic Pulmonary Fibrosis. NAC also has a mucolytic effect which makes it particularly useful for treatment of these pulmonary diseases. The effect of oral NAC has been tested in these indications in several clinical trials providing extensive safety data. In COPD, NAC 600mg bid improves airway function and reduces the frequency of acute exacerbations.[14, 15] Doses of up to 1800mg/day have been well-tolerated in the treatment of Idiopathic Pulmonary Fibrosis.[16] Paracetamol (acetaminophen) toxicity is treated with a loading dose of 140 mg/kg NAC followed by 70 mg/kg every 4 hours for 17 doses.[17] Normal volunteers tolerated a dose of 11.2 grams NAC/day for three months without any serious undesirable effects [18] and in another study a dose of 500mg/kg/day was tolerated.[19] The most frequent adverse events associated with the oral administration of NAC are

gastrointestinal in nature and include vomiting, diarrhea, stomatitis, abdominal pain and nausea (incidence rate $\geq 1/1000$ to $< 1/100$). Hypersensitivity reactions including anaphylactic shock and anaphylactic/anaphylactoid reaction (incidence rate $< 1/10,000$), dyspnea, bronchospasm (incidence rate $\geq 1/10,000$ to $< 1/1000$), angioedema, tachycardia, urticaria, rash and pruritus (incidence rate $\geq 1/1000$ to $< 1/100$) have been reported less frequently. Finally, reports of headache, tinnitus, pyrexia, blood pressure decreased (incidence rate $\geq 1/1000$ to $< 1/100$), face edema and hemorrhage have also been collected with oral NAC. In this study, we will use NAC 600 mg effervescent tablets which are generally more pleasant and more tolerable than large capsules; however, because the formulation contains sodium, we will exclude patients with uncontrolled arterial hypertension defined as diastolic blood pressure > 95 mm Hg or systolic blood pressure > 160 mm Hg.

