3. STUDY DESIGN

3. DESCRIPTION OF THE STUDY

This study is a phase 1 dose escalation study with 3 cohorts, designed to assess the safety and tolerability of NAC in subjects with RP. Thirty subjects with RP will be enrolled from the clinic population of the Wilmer Eye Institute, Johns Hopkins. Informed consent will be obtained from all study subjects prior to enrollment. Each cohort will have an experimental and an exploratory arm. Subjects with RP will be enrolled in the experimental arm if they have a high carbonyl content (≥ 0.6) and a reduced GSH/GSSG ratio (≤ 3.0) in the aqueous. Subjects with RP who don't have a high carbonyl content (≥ 0.6) and a reduced GSH/GSSG ratio (≤ 3.0) but otherwise are good candidates for the study will be enrolled in the exploratory arm. The reason for this stratification is that the primary outcome is the change from baseline carbonyl content and GSH/GSSG caused by each dose of NAC and patients who have reduced chance to show improvement could skew the data and reduce the ability to identify the minimally effect dose. In a previous study, 17 of 20 patients with RP fit these criteria, so we anticipate that 8-9 subjects in each cohort will be in the experimental group. We do not want to

completely exclude RP patients who do not fit these criteria, because they may experience substantial decrease in carbonyl content and substantial increase in GSH/GSSG and their inclusion in the exploratory arm will help to determine if patients who do not fit the criteria should be excluded from the next trial, a longer trial with a functional endpoint.

Baseline testing will include: (1) detailed medical and ophthalmological history, (2) measurement of vital signs (3) slit lamp examination, (4) funduscopy examination, (5) best-corrected visual acuity (BCVA), (6) MP1 and MAIA microperimetry, (7) SD-OCT, and (8) ultrawide angle fundus photographs. One eye will be selected as the study eye and an anterior chamber tap will be done for measurement of GSH/GSSG and protein carbonyl content. Serum GSH/GSSG, protein carbonyl content and bilirubin levels will also be measured. Blood will be obtained for RNA and DNA samples. The following is the dosing of NAC 600 mg effervescent tablets in each cohort.

	Baseline	Week 4	Week 8	Week 12	Week 20	Week 24
Cohort 1	600mg bid	600mg bid	600mg bid	600mg tid	600mg tid	600mg tid
Cohort 2	1200mg bid	1200mg bid	1200mg bid	1200mg tid	1200mg tid	1200mg tid

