Cohort 3	1800mg bid	1800mg bid	1800mg bid	1800mg tid	1800mg tid	1800mg tid

There will be 8 study visits (screening, baseline and month 1-6), all study visits after the baseline visit will be 28±7 days apart, followed by a 12 week observation period. At each visit, patients will have medical history, measurement of vital signs (blood pressure, heart rate, respiratory rate and temperature), review of concomitant medications, review of study drug diary, recording of adverse events, BCVA, eye examination, and anterior chamber tap. MP1 microperimetry will be done at screening and baseline visit. Optical Coherence tomography will be done at the screening and baseline visit and repeated every 3 months. MAIA microperimetry will be done at screening and baseline visit and repeated every month. Fundus autofluorescence and Ultrawide field fundus photographs will be obtained at screening and month 6 visit. At all visits where needed, microperimetry will be performed first followed by OCT, FAF and UWFP. Serum levels of NAC pre- and post-dose will be measured at baseline, week 12 and 24. When all 10 subjects in cohort 1 have had a week 4 visit, the PI will review safety and tolerability with study team members and if there has been good safety and tolerability, enrollment will begin for cohort 2. When all 10 subjects in cohort 2 have had a week 4 visit, the PI will

review safety and tolerability with study team members and if there has been good safety and tolerability, enrollment will begin for cohort 3.

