5.3.5 Plans to Decrease Potential Risks and Increase Safety

Detailed ocular examinations (e.g., VA, slit lamp examination and dilated fundus examination) will be performed every month. The Principal Investigator will review all adverse events. The appropriate IRB will be notified immediately of any serious adverse events and will be notified in yearly renewals of all other adverse events. The IRB and FDA will be notified of any interruption in enrollment or change in the conduct of the study. Study drug administration will be held for subjects who experience certain systemic or ocular adverse events related to the drug. In the event any subject develops an adverse event in the study eye that is considered by the designated evaluating physician to be severe in intensity, serious consideration should be given to withdrawing the subject from the study.

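### A declared MTD governs only later enrollees, so if a tid dose fails after the next cohort has opened, that cohort's scheduled week-12 increase still stands

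*Combined protocol and SAP*

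**What the plan says.** Section 4.3 lists six doses in ascending order: 600 mg bid, 600 mg tid, 1200 mg bid, 1200 mg tid, 1800 mg bid and 1800 mg tid. A dose fails when 3 of a cohort's first 5 subjects, or 5 in all, cannot tolerate it. Then "no additional subjects will be treated with that dose and the dose immediately below it will be designated the maximum tolerated dose". The next sentence says who receives that dose: "All subsequent subjects enrolled in the study will be treated with the maximum tolerated dose".

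Separately, for a subject who cannot tolerate the assigned dose because of nausea or vomiting, "the dose will be reduced to the dose immediately below the current dose". This repeats until a dose is tolerated, and the subject then stays on that dose for the rest of the trial.

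Section 3 (Description of the Study) fixes the schedule in a table introduced by "The following is the dosing of NAC 600 mg effervescent tablets in each cohort". Each cohort takes its dose bid from baseline and tid from week 12. Cohort 2 depends on this condition: "When all 10 subjects in cohort 1 have had a week 4 visit, the PI will review safety and tolerability with study team members". Cohort 3 depends on the same condition applied to cohort 2.

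**The concern.** The last subject of a cohort reaches tid dosing eight weeks after the week-4 visit that allows the next cohort to open. A tid dose can therefore fail while next-cohort subjects are already on drug. Their dose is set by cohort at enrollment, and the MTD sentence reaches only people enrolled afterwards. Followed as written, the schedule raises them further above a dose the trial has just declared the maximum tolerated.

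Safety and tolerability is the primary outcome (Section 3.2.1). A tolerability rule should give the intended instruction when it is triggered, without relying on someone to override the dosing table.

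**Working it through.** The plan states no figure on this point, so there is none to reproduce. The check has four steps.

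**1. Doses (Section 3 table, Section 4.3 order).** Daily total = tablet dose × times per day.

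| Failed dose | MTD | Next cohort before week 12 | Next cohort from week 12 |
|---|---|---|---|
| 600 mg tid (1800 mg/day) | 600 mg bid (1200) | 1200 mg bid (2400); 2400/1200 = 2.0 × MTD | 1200 mg tid (3600); 3600/1200 = 3.0 × MTD |
| 1200 mg tid (3600 mg/day) | 1200 mg bid (2400) | 1800 mg bid (3600); 3600/2400 = 1.5 × MTD | 1800 mg tid (5400); 5400/2400 = 2.25 × MTD |

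The bid dose is therefore already above the MTD, and week 12 widens the gap. Against the failed dose, the comparison is milder: 2400 exceeds 1800, and 3600 equals 3600.

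**2. Who still rises.** The bar on the failed dose covers 600 mg tid or 1200 mg tid. It protects same-cohort subjects who have not yet reached that dose, but the next cohort is due to receive a different dose. A next-cohort subject already reduced for intolerance stays reduced and does not rise. Those left are enrolled next-cohort subjects who have tolerated their bid dose.

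**3. How often a tid dose fails.** Let p be the share of subjects unable to tolerate it. The documents do not give p, so it is assumed, with all 10 subjects reaching tid and acting independently.

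P(fail) = P(at least 3 of first 5) + Σ over a = 0, 1, 2 of P(a of first 5) × P(at least 5 − a of last 5)

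At p = 0.20: 0.0579 + 0.2048 × 0.0579 + 0.4096 × 0.0067 + 0.3277 × 0.0003 = 0.0726.

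| p | 1% | 10% | 20% | 30% |
|---|---|---|---|---|
| P(fail) | 0.001% | 0.9% | 7.3% | 22.5% |

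**4. How often it fails after the next cohort's first dose.** Section 4.1.1 expects enrollment to take 12 months, and Section 3.3 puts screening 28 to 56 days before baseline (s = 4 or 8 weeks). With even accrual, each cohort takes A = (52 − 2(4 + s))/3 = 12 or 9.33 weeks, and the next cohort's first dose falls at A + 4 + s = 20 or 21.33 weeks. Simulation used 400,000 runs per setting, first doses evenly spaced across A, and onset of intolerance uniform over the first weeks of tid:

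| p | Onset within 2–4 weeks | Onset over 12 weeks |
|---|---|---|
| 10% | 0.06–0.24% | 0.7–0.9% |
| 20% | 1.1–2.5% | 5.8–6.6% |
| 30% | 4.3–8.9% | 18–21% |

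When this happens, 1.4 to 5.1 next-cohort subjects are on drug on average, a count that includes the occasional subject already past week 12. The short-onset figures depend on spacing. With first doses A/10 weeks apart, the lower bounds drop from 1.1% to 0.5% (p = 20%) and from 4.3% to 1.9% (p = 30%).

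If a cohort instead fills in 4 weeks with 4-week screening, the next cohort's first dose falls at 4 + 4 + 4 = 12 weeks, exactly when tid begins. Every tid failure then comes after it, so the chance is the full P(fail), with about 7 to 10 subjects on drug (simulated at p = 20%). This pace completes enrollment in 3 × 4 + 2 × 8 = 28 weeks, faster than Section 4.1.1 expects.

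**The case against.** The strongest reply is that the people affected have largely shown they can cope. An intolerant subject is stepped down and stays down, so only those tolerating bid dosing move up, and they have already taken at least the failed dose's daily total. This is correct and sets the size of the point. It does not show that they tolerate the next step, and the cohort-level rule has just advised against going higher.

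A second reply is that supervision would catch it. The principal investigator reviews adverse events continuously (Section 3.3), the study can be terminated (Section 4.4), and declaring an MTD may well count as a change in study conduct that must go to the IRB and FDA (Section 5.3.5). Also, "Study drug administration will be held for subjects who experience certain systemic or ocular adverse events related to the drug". These provisions make an unexamined increase less likely. They are discretionary or respond to a subject's own events, and none instructs anyone to cancel the increase for a subject who is tolerating treatment.

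A third reply is that NAC is well tolerated. Section 1.1 (Study Rationale) puts gastrointestinal events at 1/1000 to under 1/100, though not for these regimens specifically, and reports: "Normal volunteers tolerated a dose of 11.2 grams NAC/day for three months without any serious undesirable effects". The top dose here is 5.4 g/day. This supports a low probability, and the 20% and 30% rows have no source in the documents. Still, Section 4.3 treats each tid regimen as a dose that can fail, so the rule should work if one does.

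A reader might also infer that an intolerant next-cohort subject would be stepped down onto the dose just closed. The text does not settle this. If the bar on the failed dose covers enrolled subjects, that dose is unavailable and the subject would go lower. No weight is placed on it.

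**Conclusion.** The gap is real and minor. If 600 mg tid or 1200 mg tid fails after the next cohort has started, enrolled subjects of that cohort who have not been reduced remain scheduled to go from 2.0 to 3.0 times the MTD, or from 1.5 to 2.25 times.

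The gap in the text is certain; its frequency is not. Frequency rests on assumed intolerance, onset and accrual. At 10% intolerance it stays below 1% under either accrual pattern.

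Three stronger readings are not supported:
- **The failure rule protects nobody already enrolled.** It does bar the failed dose for same-cohort subjects who have not reached it.
- **Subjects are exposed to a known hazard.** Nothing in the documents shows this, and those who rise have tolerated a comparable or higher daily total.
- **The analysis is compromised.** Nothing in Section 4.5 uses the MTD.

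The week-4 condition for opening a cohort and the order of the six doses are not in question.

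**What to change.** Add to Section 4.3:

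> Once an MTD is declared, no enrolled subject is stepped up above it; the PI reviews and documents whether subjects already above it continue at their current dose or are reduced to the MTD.

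This cancels the automatic increase and leaves to documented judgment whether a subject who tolerates a dose above the MTD should be lowered, which is debatable. It adds no subjects, visits or delay.

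The cost arises only after an MTD is declared. Each capped subject loses up to 3 aqueous samples on the planned tid dose (weeks 16, 20 and 24), out of 3 × 10 = 30 per cohort. Under 12-month accrual that is about 3 × 1.4 = 4 to 3 × 5.1 = 15 of 30. Under fast accrual it is about 3 × 7 = 21 to 3 × 10 = 30. If the PI lowers a subject before week 12, the remaining samples on the planned bid dose are lost as well. The biomarker comparison by dose would be thinner, which matters because Section 3 describes its aim this way: "the primary outcome is the change from baseline carbonyl content and GSH/GSSG caused by each dose of NAC".

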4.4 STUDY DISCONTINUATION

The Wilmer Eye Institute may terminate this study at any time. Reasons for terminating the study may include the following:

- The incidence or severity of adverse events in this or other studies indicates a potential health hazard to subjects
- Subject enrollment is unsatisfactory

4.5 STATISTICAL METHODS

4.5.1 Safety Analysis

The primary outcome measure is the safety and tolerability of N-acetyl cysteine (NAC) in patients with RP. Adverse events and results of ocular examinations from all 30 patients will be utilized to summarize safety data. The number and percentage of patients with treatment emergent adverse events (i.e. started or increased in severity after the patient received study treatment and includes abnormal lab results etc) will be summarised. The adverse events recorded prior to NAC administration will not be summarised and will be separated from the adverse events that are recorded post NAC administration in the final listings.

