3.2 OUTCOME MEASURES

3.2.1 Primary Outcome Measures

- Assessment of safety and tolerability of NAC including incidence and severity of systemic and ocular adverse events (AEs) and changes from baseline vital signs and physical examination.

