5. ASSESSMENT OF SAFETY

5.1 ADVERSE EVENTS

For this protocol, an AE is any “on study” untoward medical occurrence (e.g., sign, symptom, disease, syndrome, intercurrent illness) that occurs in a study subject, regardless of the suspected cause.

Unchanged, chronic conditions are NOT AEs and should not be recorded on the AE pages of the CRF. An exacerbation or worsening of a chronic condition should be recorded as an AE.

Both serious and non-serious AEs should be graded on a three-point scale (mild, moderate, severe) and reported in detail on the appropriate AE page of the CRF.

The suggested definitions are as follows:

Mild:	Discomfort noticed but no disruption of normal daily activity
Moderate:	Discomfort sufficient to reduce or affect normal daily activity
Severe:	Incapacitating with inability to work or perform normal daily activity

Using the following criteria, investigators also need to assess whether there is a reasonable possibility that study intervention caused or contributed to the AE.

- Yes (possibly or probably)

There is a clinically plausible time sequence between onset of the AE and study intervention; and/or

There is a biologically plausible mechanism for study intervention causing or contributing to the AE;
and

The AE may or may not be attributed to concurrent/underlying illness, other drugs, or procedures.

- No

A clinically plausible temporal sequence is inconsistent with the onset of the AE and study intervention;
and/or

A causal relationship is considered biologically implausible.

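### The only summary specified for the primary safety outcome is a treatment-emergent percentage with no split by dose, severity or on-/off-drug period, and its fixed 30 does not fit the replacement rule

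*Combined protocol and SAP*

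**What the plan says.** Section 4.5.1 is the whole stated analysis of the primary outcome. It says "Adverse events and results of ocular examinations from all 30 patients will be utilized to summarize safety data". The statistic it names is "The number and percentage of patients with treatment emergent adverse events", where treatment-emergent means "started or increased in severity after the patient received study treatment". The one separation it makes is between events before and after NAC was given.

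Other sections bear on this:

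- **Doses.** Section 4.3: "This is a dose-escalation study in which 6 doses of NAC effervescent tablets are being tested". The dosing table in section 3 moves each cohort from bid to tid at week 12, so each patient is scheduled for two regimens. Section 4.3 also allows step-down for intolerance, as far as 600 mg once daily.
- **Outcome.** Section 3.2.1 defines the primary outcome as safety and tolerability, "including incidence and severity of systemic and ocular adverse events (AEs"), together with changes in vital signs and physical examination.
- **Data collected.** Section 5.1 has every AE graded on three levels of severity, and "investigators also need to assess whether there is a reasonable possibility that study intervention caused or contributed to the AE".
- **Time.** Appendix A marks NAC treatment up to week 24, and paracentesis and AE recording up to week 36. Section 3.3 continues AE recording for 14 days after the last visit.
- **Numbers.** Section 4.1.1 enrols thirty subjects. Section 4.5.6 replaces anyone terminated before week 24.

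**The concern.** A dose-escalation study exists to say how tolerability changes with dose, and section 3 expects a longer trial with a functional endpoint to follow. If section 4.5.1 is followed as written, the reported primary result would be a percentage over all patients. It would mix regimens from 1200 to 5400 mg/day, mild with severe events, and events on NAC with events weeks after it stopped. A reader could not tell from it whether tolerability worsened at the higher doses.

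The denominator raises a smaller question. The plan fixes it at 30, but another section lets the number of people exposed exceed 30. It does not say whether a dosed and then replaced subject belongs to the safety set. Subjects who left because of the drug are among those affected.

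**Working it through.** **1. The plan's own figure.** Section 3 has three cohorts and gives 10 subjects each for cohorts 1 and 2. With a total of 30, cohort 3 also has 10. So 3 × 10 = 30, which reproduces the stated denominator when no dosed subject is replaced.

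**2. Dose range.** Daily doses from section 4.3 are 2 × 600 = 1200, 3 × 600 = 1800, 2 × 1200 = 2400, 3 × 1200 = 3600, 2 × 1800 = 3600 and 3 × 1800 = 5400 mg. The ratio of highest to lowest is 5400/1200 = 4.5.

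**3. What a pooled percentage can hide.** Take 9 of 30 patients with a treatment-emergent AE (illustrative). Intervals are exact (Clopper-Pearson) 95%.

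| Pattern by cohort | Pooled | Cohort 3 alone |
|---|---|---|
| 3/10, 3/10, 3/10 | 9/30 = 30% (14.7 to 49.4%) | 3/10 = 30% (6.7 to 65.2%) |
| 0/10, 1/10, 8/10 | 9/30 = 30% (14.7 to 49.4%) | 8/10 = 80% (44.4 to 97.5%) |

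The pooled result is identical in a flat and a steep dose pattern.

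**4. What zero events would mean.** With no events among n patients, the upper limit of the two-sided 95% interval is 1 − 0.025^(1/n).

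- n = 30: 1 − 0.025^(1/30) = 11.6%.
- n = 10: 1 − 0.025^(1/10) = 30.8%.

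The pooled limit is not evidence about any one cohort.

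**5. Why cohort alone is not enough.** Each cohort contains a bid and a tid phase. Step-down moves individuals to lower regimens, and under section 4.3 subjects enrolled after a maximum tolerated dose is declared receive that dose. The cohort entered therefore does not identify the regimen in use when an AE began; dose at onset does.

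**6. The open window.** NAC runs to day 168 (week 24). The last visit is day 252 (week 36), and recording can run to 252 + 14 = 266. The off-drug part is 266 − 168 = 98 days. Suppose events unrelated to NAC occur at a constant rate and a proportion p of patients has had one by day 168. By day 266 the proportion is 1 − (1 − p)^(266/168). The documents give no background rate, so p is an assumption:

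| p by day 168 | By day 266 |
|---|---|
| 10% | 15% |
| 20% | 30% |
| 40% | 55% |

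The statistic counts patients with at least one event, so added follow-up can only raise it.

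**7. Denominator.** If k dosed subjects are replaced, 30 + k people are exposed. The documents give no termination rate. At an assumed 5% to 20% before week 24, all after a first dose, 30/(1 − 0.05) = 31.6 to 30/(1 − 0.20) = 37.5, or about 32 to 38 people. Subjects who leave before a first dose add no exposed person.

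**The case against.** The strongest reply is that pooling is inferred from silence. The sentence about all 30 patients says whose data contribute, not that the cohorts are merged into one column. Section 4.5.1 also mentions ocular examination results and final listings, and severity is already committed to in sections 3.2.1 and 5.1. This is right as far as it goes: cohort tables are not forbidden. But none is planned, and the one named statistic does not use dose, severity or relatedness.

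Second, decisions that depend on dose do not use this percentage. Escalation rests on the week-4 reviews in section 3. The maximum tolerated dose rests on the rule in section 4.3, which acts if 3 of a cohort's first 5 subjects, or "a total of 5 subjects are unable to tolerate a particular dose of NAC". This stands. A reader might infer that escalation is compromised; the documents do not support that. Nor should that limit be set against the pooled percentage, because it counts intolerance and section 4.5.1 counts any treatment-emergent AE.

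Third, follow-up after week 24 is not free of study procedures, since taps and blood draws continue, so those events should be counted. That also stands; the point is to show them separately. A reader might further infer that drug-free time dilutes a signal at the top dose. It does not, because the percentage of patients ever affected is cumulative.

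Fourth, section 4.5.4 bases safety analyses on available cases, and section 4.5.6 asks withdrawn subjects to return for assessment and observation. Both lean towards keeping replaced subjects' data. A reader might infer that their events will be dropped; the text does not say so.

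**Conclusion.** The concern holds as a gap in the planned reporting of the primary outcome, and it should be fixed. As specified, the percentage cannot distinguish a flat from a steep dose pattern (9/30 in both examples). When no events occur, it gives an upper limit of 11.6% where a single cohort supports only 30.8%. The open window can add background events, taking 20% to 30% in the main illustration. Event patterns and background rates here are assumptions, and the cohort figures assume 10 subjects each.

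The denominator is an inconsistency between sections 4.5.1 and 4.5.6 that arises only if a dosed subject is replaced. No bias is shown. Trial conduct, escalation and the maximum-tolerated-dose rule are not affected.

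**What to change.** Amend section 4.5.1 as follows:

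- Define the safety set as every subject who received at least one dose of NAC, including those later replaced. Report the number of exits before week 24 and the reasons.
- Tabulate AEs by cohort entered and by dose at onset, using subjects ever on that dose as the denominator. Show severity grade and recorded relatedness.
- Report on-drug events, from first dose to last dose plus a short lag stated in advance, separately from post-treatment events. The lag keeps a reaction to the week-24 clinic dose in the on-drug count. Post-treatment events are still reported because taps continue.
- Keep the pooled percentage as a total.
- Call dose comparisons descriptive: within a cohort tid always follows bid, so dose is confounded with time and with the number of taps.

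The cost is a few sentences and some table columns, using data already collected. The drawback is small cells: about 10 subjects per regimen, so limits will be wide.

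### Tolerability is part of the primary outcome, but section 4.5.1 plans no summary by dose of who was stepped down or exited

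*Combined protocol and SAP*

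**What the plan says.** Section 4.5.1 states: "The primary outcome measure is the safety and tolerability of N-acetyl cysteine (NAC) in patients with RP". Sections 2.1 and 3.2.1 agree. Section 3.2.1 describes the outcome through the incidence and severity of adverse events and changes in vital signs and physical examination.

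Section 4.3 lists six doses and says what happens when nausea or vomiting makes one intolerable: "the dose will be reduced to the dose immediately below the current dose". The step is repeated if needed: "This will be done until a tolerated dose is identified and the patient will be maintained on that dose throughout the trial". At the bottom of the ladder: "If a patient cannot tolerate a dose of 600mg qd, they will be exited from the trial". The same section has a count-based rule. "If 3 of the first 5 subjects in a cohort or a total of 5 subjects are unable to tolerate a particular dose of NAC", that dose is given to no further subjects and the one below is named the maximum tolerated dose.

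The dosing table in section 3 puts every subject on a bid regimen through week 8 and on tid from week 12. Section 3 also has the principal investigator review safety and tolerability once all 10 subjects in cohort 1, and later cohort 2, have had a week 4 visit. It sets no numerical criterion.

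On analysis, section 4.5.1 says: "Adverse events and results of ocular examinations from all 30 patients will be utilized to summarize safety data". The statistic it names is "The number and percentage of patients with treatment emergent adverse events". Section 4.5.4 uses available cases. Section 4.5.6 replaces subjects who are terminated before week 24.

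**The concern.** A patient who has nausea but takes the full dose throughout, and a patient who has nausea and is stepped down early, each add one to the count of patients with an event. The second patient's later events then arise on a lower dose but go into the same summary. Section 4.5.1 names no split by dose or cohort, so six regimens share one percentage.

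The trial is meant to say which NAC doses patients with RP can take, and to inform the choice of dose for a longer trial. A percentage with any adverse event does not answer that. The information that does, who stayed on the dose and who did not, has no planned summary anywhere in section 4.5.

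**Working it through.** The plan gives no rate, precision or power for tolerability, so there is no figure to reproduce. The power statement in section 4.5.3 concerns aqueous carbonyl content.

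**1. Outcome against analysis**

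| Element of tolerability | Where it arises | Summarised in 4.5? |
|---|---|---|
| Step-down by one or more levels | 4.3 | No |
| Exit after failing 600 mg qd | 4.3 | No |
| Dose actually taken | 3 (bid, then tid), 4.3 | No |
| Adverse-event severity | 3.2.1, graded in 5.1 | Not named |
| Subjects who leave and are replaced | 4.5.6 | Not addressed; 4.5.1 refers to 30 patients |
| Adverse events, any | 3.2.1 | Yes, pooled |

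If k subjects leave before week 24 and are replaced, 30 + k are treated. Section 4.5.1 does not say which 30 are meant.

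**2. How much the section 4.3 rule catches**

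Inputs: cohort size 10 (section 3) and the rule of 3 of the first 5, or 5 in total (section 4.3). Assumptions: all 10 start the dose, subjects are independent with a common true intolerance rate p, and the total of 5 is counted within the cohort. The documents do not give p, so a range is shown.

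Let X and Y be the numbers intolerant among the first and last five, each Binomial(5, p). Then

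P(trigger) = P(X ≥ 3) + Σ over x = 0, 1, 2 of P(X = x) · P(Y ≥ 5 − x).

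- p = 0.3: 0.1631 + 0.1681 × 0.0024 + 0.3602 × 0.0308 + 0.3087 × 0.1631 = 0.225
- p = 0.4: 0.3174 + 0.0778 × 0.0102 + 0.2592 × 0.0870 + 0.3456 × 0.3174 = 0.451

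| True intolerance rate | Rule triggers | Dose escapes |
|---|---|---|
| 10% | 0.01 | 0.99 |
| 20% | 0.07 | 0.93 |
| 30% | 0.22 | 0.78 |
| 40% | 0.45 | 0.55 |
| 50% | 0.69 | 0.31 |
| 60% | 0.87 | 0.13 |

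Five or more intolerant of 10 always triggers, so the largest count that can go unflagged is 4. Even 4 does not always escape. If the four fall in random order, at least three are in the first five with probability [C(5,3)·C(5,1) + C(5,4)·C(5,0)] / C(10,4) = (50 + 5)/210 = 0.26.

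**3. What the planned summary would show**

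Suppose 8 of 10 subjects have a treatment-emergent event at each of two doses (an assumed count). Exact Clopper-Pearson limits are the α/2 quantile of Beta(x, n − x + 1) and the 1 − α/2 quantile of Beta(x + 1, n − x).

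- Event summary: 8/10 at both doses, 80% (44.4 to 97.5%).
- Intolerance at the first dose: 0/10, 0% (upper limit 1 − 0.025^(1/10) = 30.8%).
- Intolerance at the second dose: 4/10, 40% (12.2 to 73.8%).

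The event rows are identical even if a split by cohort is added. The intolerance rows are not.

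**The case against.** The strongest reply is that the protocol judges tolerability outside section 4.5.1. The section 4.3 rule counts intolerant subjects and names a maximum tolerated dose, and the principal investigator reviews tolerability before cohorts 2 and 3 open. This stands as far as it goes: a dose that half or more of a cohort visibly cannot take will be flagged. A reader might infer that the trial cannot say anything about which doses are tolerated, or that a dose most subjects fail could pass unseen. The documents do not support either.

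What the reply leaves open is everything below the trigger. The rule is a stopping device and yields no rate or interval. The review has no numerical criterion and is timed to week 4, in the bid period, so it need not cover the tid doses.

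A second reply is that adverse-event severity, graded in section 5.1 by effect on daily activity, would separate mild nausea from nausea that forces a reduction. It would help, but section 4.5.1 does not name a severity summary. The recording instructions in sections 5.1 and 5.3.1 cover severity and causality without mentioning action taken with study drug.

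Third, it is tempting to argue that nausea will be reported at every dose, so event percentages are bound to be uninformative. The documents do not say that. Section 4.3 calls nausea and vomiting the most common side effect, while the Study Rationale puts gastrointestinal events on oral NAC at 1/1000 to below 1/100. The point needs only that event counts can be similar while step-downs differ.

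**Conclusion.** The point holds in a bounded form. Part of the primary outcome has no planned analysis: nothing in section 4.5 summarises step-downs, exits or dose taken, and section 4.5.1 does not separate the six regimens. The undetected case is at most 4 of 10 subjects per dose. At true intolerance of 30% to 40% the section 4.3 rule stays silent with probability 0.78 to 0.55, under the independence and cohort-of-10 assumptions above. The example of 0/10 against 4/10 with equal event counts is an illustration, not a forecast.

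Three further inferences go beyond the text. Section 4.5.1 does not count adverse events alone, since it also uses ocular examinations, though these do not measure whether an oral drug is tolerated. The plan does not state that replaced subjects will be dropped; it leaves the denominator open, so intolerant exits could be lost. And section 4.3 prescribes the step-down without saying how it is recorded, so it cannot be taken as given that the data are already captured.

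None of this questions the dosing or stopping rules, only how their results are reported.

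**What to change.** Add to section 4.5.1, as part of the primary outcome, one table by assigned regimen with bid and tid periods separate:

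- number who started the regimen, stayed on the full dose, were stepped down, and exited;
- proportion intolerant (stepped down or exited) with an exact 95% CI;
- every treated subject kept in the denominator, including those later replaced;
- for tid regimens, the number who never started because they had been stepped down during the bid period.

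State that adverse events are attributed to the dose being taken at onset, and tabulate them by that dose with severity, as section 3.2.1 implies.

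A Kaplan-Meier curve of time to first step-down or exit is optional. With 10 subjects per cohort and a planned bid-to-tid switch, its time origin and censoring would need defining, and the counts carry most of the information.

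The cost is one table and a few sentences, plus a check that the study drug diary or CRF records the date and size of each dose change. Section 3 mentions diary review, but the documents do not describe its content and Appendix A has no row for it. If dose changes are not recorded, a CRF field is needed.
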